### **2.5.3 *In vivo* activity of DHA in a canine oral mucosa model**

To determine whether *in vitro* activities of DHA shown in previous sections were applicable *in vivo*, a canine oral papillomavirus (COPV) model was used. This animal model emulates the effects of HPV on the mucosal sites in human [41] and has been previously used for efficacy evaluation of papillomavirus vaccines. In this model, 100% of challenged animals become infected and develop tumors. Canine oral papillomas have an incubation period of 4–8 weeks following inoculation, and typically undergo spontaneous regression in the ensuing 4–8 weeks [42].

The maxillary buccal mucosae of six 10-week-old, female beagles were abraded with a sterile wire brush. Wart homogenate containing 500 ng (based on L1 concentration) of oncogenic COPV was then applied to the excoriated mucosa with a cotton swab. After 24 hours, the infected areas of three beagles were treated topically with 2.22 mg DHA dissolved in 100  $\mu$ L dimethyl sulfoxide (DMSO) (78 mM). The infected areas of the other three beagles were treated with 100  $\mu$ L DMSO as the placebo control. Treatment was applied once daily, five times a week, for 6 weeks.

Figure 4A depicts a schematic of viral challenge, drug treatment, tumor appearance, and tumor regression. In all control animals, tumors appeared approximately 3 weeks after the COPV challenge. Figure 4B is a photograph of virus-infected dogs treated with DMSO (left) or DHA (right) at 6 weeks post-challenge. The tumor shown in the DMSO-treated dog is representative of the size of tumors observed in all tumor-positive dogs and was taken at the pinnacle of tumor growth. The DHA-treated dog is free of tumor. In addition, the oral mucosa treated with DHA shows no evidence of ulceration or inflammation, consistent with the lack of DHA cytotoxicity for normal epithelial cells *in vitro*. All tumors were regressed by 8 weeks following initial viral challenge. Study animals were observed for another week after regression to ensure that no additional tumors were formed. Peripheral blood was obtained 1, 3, and 5 weeks after the onset of tumor formation.

Figure 5A summarizes the results of tumor formation in the six study dogs. All virus-infected dogs treated with DMSO developed tumors at 3 to 4 weeks post-challenge. In contrast, DHA treatment abolished tumor formation in two of three infected animals. The lesions that developed in the DHA-treated animal (dog 5) underwent regression 2 weeks earlier than those in the animals treated with DMSO alone, although the mass was of comparable size to those in control animals.

[figure not shown]
**Figure 4.** Topical therapeutic effect of DHA in a preclinical papillomavirus model. **(A)** a schematic representation of the experimental protocol. Treatment was initiated 24 hours after the COPV challenge and stopped when all tumors had regressed. For this COPV model, tumors appeared approximately 3 weeks after viral challenge and all tumors had regressed 8 weeks post-challenge. **(B)** Representative images of dogs with and without tumor formation.

Although the study sample size was small, precluding statistical analysis, it should be emphasized that the COPV model resulted in a 100% tumor formation rate during decades of working with this model by the group. Thus, the absence of tumors in 2 of 3 treated animals is biologically significant, suggesting that DHA is effective in the prevention of tumor formation.

Visual observations of the oral mucosa approximately 3 weeks post-challenge identified a similar mucosal “roughness” in all of the challenged dogs, including the DHA-treated animals, indicative of early papilloma formation. We postulated that DHA might be inhibiting tumor formation rather than virus infection.

To determine whether the DHA-treated dogs had a subclinical viral infection, serum samples obtained at the end of the trial were used to detect and quantify antibody responses to the L1 viral capsid protein. Serum samples were analyzed for papillomavirus antibody using an ELISA immunoassay. The results are shown in Figure 5B. Despite the finding that only one DHA-treated dog developed a tumor, all DHA-treated animals developed antibody titers against the L1 protein, suggesting that the tumor-free animals indeed had been infected with virus and that the virus had replicated and synthesized significant amounts of L1 protein. These data suggest that DHA inhibits tumor formation rather than viral replication. As anticipated, all of the

control animals also developed antibodies to L1, which is normally observed during the natural regression of these tumors.

**Figure 5.** Topically applied DHA inhibits papilloma formation by COPV. **(A)** Tabulation of tumor formation in dogs. All 3 control animals and 1 DHA-treated animal developed tumors that reached a similar size to those shown in Figure 4B, left. The tumor in the DHA-treated dog regressed 2 weeks sooner than the tumors in DMSO-treated dogs. **(B)** ELISA results from dog serum collected during the last week of the study. All dogs were positive for antibodies against L1, indicating an initial infection in all dogs. Dogs 4 and 6 without the presence of tumors showed antibodies against L1, suggesting DHA can inhibit tumor formation without inhibiting the initial infection or replication of the virus.

In summary, and taking into account the large body of clinical experience garnered from the use of systemically administered Artesunate for the treatment of acute malaria, these data provide rationale for the use of a topical formulation of Artesunate in the treatment of incipient, intraepithelial neoplasia caused by HPV.

### **3.0 CLINICAL SAFETY AND TOLERABILITY**

Commercially available Artesunate has been used for the treatment of acute malaria for decades using systemic dosing that is at least 5-fold higher than the suppository dosing proposed in this clinical trial. Rectal suppository formulations are approved for use as a second-line treatment for acute malarial infections in children, and used off-label in adults, who cannot tolerate oral administration and are distant from a hospital setting [4]. For severe malaria during pregnancy, there is less certainty about the safety of Artesunate during the first trimester, but Artesunate is recommended as first-line therapy during the second and third trimesters [43]. Two reports submitted to the FDA by the WHO and Novartis summarize many of the safety studies conducted with artemisinin and its derivatives, including Artesunate [4, 17, 18, 29].

For young children of less than 5 years of age, rectal Artesunate suppository administered at a single dose of 10 mg/kg is the only WHO recommended safe pre-referral treatment for severe malaria. Rectal suppository dosing has also been tested in adults, including regimens of 500 mg/day for 5 consecutive days [44]. No local or serious systemic side effects have been reported at these doses. The initial starting intravaginal suppository doses proposed, 50 mg ( $\leq 1$  mg/kg in individuals who weigh  $\geq 50$  kg, a subject inclusion criterion for this study) and the highest proposed dose, 200 mg ( $\leq 4$  mg/kg) are approximately 10 and 2.5-fold lower than the approved pediatric rectal suppository dose.

### **3.1 Clinical Toxicology and Pharmacology**

Clinical effects reported in subjects treated with artemisinin compounds have included mild gastrointestinal disturbances, dizziness, and tinnitus, albeit with weak evidence of association [45]. There have also been reports of transient reticulocytopenia, neutropenia and elevated liver enzyme values, though none has been considered to be of clinical significance [45]. Electrocardiographic abnormalities such as bradycardia and prolongation of the QT interval, have been reported but again, no impairment of heart function has been observed in numerous malarial therapy trials in humans [24, 45]. The only potentially serious adverse effects that have been convincingly associated with administration of artemisinin compounds are the type 1 hypersensitivity reactions in approximately 1 in 3000 patients [46]. In nonclinical studies in mice, CNS effects have been observed; however, such effects have not been observed in humans. Because the dosage evaluated in mice (100 mg/kg, i.m., artemotil and artemether) is at least 6 fold higher than therapeutic doses in humans, these toxicities are likely of little clinical relevance (see nonclinical toxicology section 2.4 above).

With regard to strong nonclinical evidence of artemisinin compounds-induced embryotoxicity, the tight relationship to a specific period of the gestational cycle has informed the contraindication of their usage during the first trimester of pregnancy in humans [29, 32]. Importantly, in malaria treatment, there is no evidence for adverse effects on the fetus following exposure during the second and third trimesters, when these drugs are recommended depending on the safety profile of the partner drug in the artemisinin-based combination treatment [45]. This recommendation can be

sidestepped in cases of severe malaria where artemisinin derivatives are clearly superior in terms of life-saving efficacy [45]. Prospective tracking of over 1000 pregnancies did not reveal any significant adverse effects following artemisinins' use during the 2nd and 3rd trimesters [47, 48].

Finally, artemisinins are generally well tolerated and human studies with the various drugs used in combinatorial therapy against malaria have not revealed major clinical concerns regarding untoward drug interactions. However, because such interactions are peculiar to the compounds themselves, each potential drug interaction has to be considered on its own [18, 49].

In this clinical protocol, intra-vaginal Artesunate suppositories will be tested. Direct application to the mucosal surface at the doses we propose is unlikely to result in significant systemic absorption. While there are no published pharmacologic data for intra-vaginal administration of Artesunate suppositories, clinical pharmacology of Artesunate and its metabolite DHA following rectal, IV, IM, and oral administration are well documented in the anti-malaria literature [4, 18, 24, 28, 50-52]. Years of pharmacokinetic data already performed with Artesunate informed the choice of intra-vaginal dosing [49-51, 53, 54]. A review of clinical toxicology and pharmacology assessments of Artesunate and its metabolite DHA is summarized in Table 1.

Artesunate is rapidly absorbed, with peak plasma levels occurring 1.5 h, 2 h and 0.5 h after oral, rectal and intramuscular administration, respectively [3, 55-58]. It is almost entirely converted to its active metabolite DHA [59]. Elimination of Artesunate is very rapid, and its activity is determined by DHA elimination, which has a half-life of approximately 45 min [11, 52].

**Table 2:** Clinical Toxicity and Pharmacology of Artesunate

Route of Administration	Dosing Regime	Toxicity Summary
Oral Administration of Arteminol-R (DHA) in patients with squamous cell carcinoma stage 3 or 4 [60]	Treatment Phase: 7 days @ 100mg/day, and if no NCI CTCAE grade 3 or 4, then additional 21 days @ 200 mg/day  Follow Up Phase: Four patients with relapse received 28 days of DHA at 200 mg/day	Treatment Phase: Zero incidence of grade 3 or 4 AEs; five patients with grade 1 or 2 AEs described as transient 'flu-like syndrome', headache, and abdominal pain
Rectal Artesunate – data from 1167 patients in 15 clinical trials	A single high dose of rectal Artesunate (10mg/kg) was 5X more likely to	Total incidence of AEs considered by clinicians to be possibly drug-related was approx. between 2.7% and 9.0% of all rectally

Route of Administration	Dosing Regime	Toxicity Summary
of rectal artemisinin derivative (Artesunate, artemisinin and artemether) therapy [61]	achieve >90% parasite reductions at 24 hours than were multiple lower doses of rectal Artesunate, or a single lower dose administration of rectal artemether.	artemisinin-treated patients, compared with 22% of quinine-treated patients. Majority of the possibly drug-related adverse events involved either the gastrointestinal system or were generalized and non-specific in nature and were not severe.
IV Administration of Artesunate in US Phase I safety trial [51]	Dose escalation of single dose of 0.5, 1, 2, 4, or 8 mg/kg over 2 min	No dose-limiting toxicity
IV Administration of Artesunate in a Phase 1b Study [50]	3 days @ 2, 4, or 8 mg/kg over a 2-min infusion	
 
• No subject drop-outs for adverse events or other treatment-related issues.
 
• Dose-related decrease in reticulocyte count noted that peaked 4 days after dosing and returned to normal by study day 7 in most cases, and day 10 in all patients.
 
• No other clinically significant laboratory abnormalities detected.
 
• No deleterious hemodynamic or ECG effects
 
• A transient, reversible sensation of altered or unusual taste, lasted 30 minutes in all cases at higher doses of Artesunate
 

IM Administration of Artesunate in Children with Severe Malaria [54]	IM 2.4 mg/kg at 0, 12, and 24 h in children from 6 months to 11 years old	No direct report of treatment-specific complications
Comprehensive review of clinical pharmacology following administration of Artesunate by the	IV Route 
 
• High initial plasma concentration subsequently declined rapidly with a half-life of less than 15 min. Clearance and volume estimates averaged 2 - 3 L/kg/hr and 0.1 - 0.3 L/kg, respectively.
 
• The metabolite DHA concentrations peaked within 25 minutes post-dose, and a half-life of 30 - 60 minutes.
 
	

Route of Administration	Dosing Regime	Toxicity Summary
IV, IM, oral or rectal routes [52]	
DHA clearance and volume averaged between 0.5 - 1.5 L/kg/hr and 0.5 - 1.0 L/kg, respectively
 
IM Route
 
 
• Lower peaks, longer half-life values, and higher volumes of distribution for Artesunate
 
• Delayed peaks for DHA; other parameters were generally similar due to the high bioavailability, assessed by exposure to DHA, associated with IM Artesunate administration (> 86%).
 
 
Oral Route
 
 
• High bioavailability of DHA (> 80%).
 
• Artesunate Cmax within 1 hour, and a half-life of 20 - 45 minutes
 
• DHA Cmax within 2 hours and a half-life of 0.5 - 1.5 hours.
 
• AUC values reported for Artesunate often substantially lower than those reported for DHA following oral administration
 
 
Rectal Route
 
 
* Similar PK results as oral administration, with the exceptions of delayed Cmax and longer half-life
 
	

Based on clinical safety studies of Artesunate in the U.S. [62], tests on daily IV boluses of up to 8 mg/kg of Artesunate did not result in dose-limiting toxicities [55]. At 8 mg/kg, a transient, reduced reticulocyte count had been observed, but resolved without intervention over a timeframe of 4-7 days [24]. Drug concentrations did not accumulate in subjects receiving multiple daily IV treatments, corroborating with known rapid elimination rates for artemisinin derivatives [50]. A significantly lower maximum plasma concentration after intra-vaginal administration is expected, compared to IV administration. This prediction is based on the pharmacokinetic studies of IM Artesunate [52], in which the rate of tissue absorption slows drug distribution; on average, one thirtieth and one fifth of Cmax observed by the IV route for Artesunate and DHA, respectively. The differences between Artesunate and its principal metabolite are due to a combination of differences in solubility, and to rapid conversion of Artesunate to DHA [52]. Despite the prediction of low systemic concentration of drug, rapid elimination following intra-vaginal administration would be expected, as seen with IM administration [52].

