**Toxicities and Adverse events**

**Table 5: Solicited General Signs and Symptoms**

Adverse Event	Short Name	Grade 1	Grade 2	Grade 3	Grade 4	Grade 5
Allergic reaction/hypersensitivity (including drug fever)	Allergic reaction	Transient flushing or rash; drug fever <38°C (<100.4°F)	Rash; flushing; urticaria; dyspnea; drug fever ≥38°C (≥100.4°F)	Symptomatic bronchospasm, with or without urticaria; parenteral mediation(s) indicated; allergy-related edema/angioedema; hypotension	Anaphylaxis	Death
Fever (in the absence of neutropenia, where neutropenia is defined as ANC <1.0 x 10  /L)	Fever	38.0-39.0°C (100.4-102.2°F)	>39.0-40.0°C (102.3-104.0°F)	>40.0°C (104.0°F) ≤24 hours	>40.0°C (104.0°F) >24 hours	Death
Cytokine release syndrome/acute infusion reaction	Cytokine release syndrome	Mild reaction; infusion interruption not indicated; intervention not indicated	Requires therapy or infusion interruption but responds promptly to symptomatic treatment (e.g., antihistamines, NSAIDs, narcotics, IV fluids); prophylactic medications indicated for ≤24hrs	Prolonged (i.e., not rapidly responsive to symptomatic medication and/or brief interruption of infusion); recurrence of symptoms following initial improvement; hospitalization indicated for other clinical sequelae (e.g. renal impairment, pulmonary infiltrates)	Life-threatening; pressor or ventilatory support indicated	Death

Nervous system disorder	Head aches	Mild pain	Moderate pain, limiting instrumental ADL	Severe pain, limiting self care, ADL	—	-
Nervous system disorder	Dizziness	Mild unsteadiness or sensation of movement	Moderate unsteadiness or sensation of movement, limiting instrumental ADL	Severe unsteadiness or sensation of movement; limiting self care ADL	—	-
Ear and labyrinth disorder	Tinnitus	Mild symptom intervention not indicated	Moderate symptoms, limiting instrumental ADL	Severe symptoms, limiting self care ADL	-	-

Patients will be monitored throughout the study for both known potential risks and for unexpected risks. During office visits, patients will be monitored specifically for any signs of:

- Symptoms of itching, burning, pain, warmth, or tenesmus
- Signs of skin breakdown including erythema, blistering, desquamation, ulceration or bleeding
- Neurologic symptoms
- Unexpected adverse events

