Subjects will be given diary cards to record local and general signs and symptoms most likely to occur between office visits. The diary cards will be collected, signs and symptoms verified, and inserted into the CRF at each subsequent visit.

Subjects who become pregnant during study will be required to discontinue the use of suppositories. Subjects removed from the study will be replaced in the treatment group. Although not considered an adverse event, pregnancy will be reported in the same way. Whenever possible, a pregnancy should be followed to term, and the status of mother and child reported. The Pregnancy Notification form will be sent by sites to the study PI ([name]) and to the sponsor (Frantz Viral Therapeutics) within 48 hours of discovery. Whenever possible, the Follow-up Pregnancy Outcome Form will be filled after delivery.

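### The solicited-symptom table does not match the protocol's own review of human effects: it omits gastrointestinal, most flu-like and taste symptoms and keeps an infusion-reaction row, so mild events of these kinds rely on unprompted reporting

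*Combined protocol and SAP*

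**What the plan says.** Safety and tolerability are the primary objective (Section 6.0). Section 7.1 assesses safety by adverse events and names symptoms to watch for: mainly local signs, plus tenesmus, bleeding and dizziness, and then any unexpected events.

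Table 5, in the unnumbered part on toxicities before Section 11.5, has six solicited rows: allergic reaction, fever, "Cytokine release syndrome/acute infusion reaction", headache, dizziness and tinnitus. Below it, the office-visit checklist includes "Symptoms of itching, burning, pain, warmth, or tenesmus", skin breakdown, neurologic symptoms and unexpected events. On the diary the protocol says: "Subjects will be given diary cards to record local and general signs and symptoms most likely to occur between office visits".

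Section 3.1 gives the human experience. Its text says: "Clinical effects reported in subjects treated with artemisinin compounds have included mild gastrointestinal disturbances, dizziness, and tinnitus, albeit with weak evidence of association". Its Table 2 adds "transient 'flu-like syndrome', headache, and abdominal pain" with the oral active metabolite. For rectal dosing it adds "Majority of the possibly drug-related adverse events involved either the gastrointestinal system or were generalized and non-specific in nature", noting that these were not severe. For repeated intravenous dosing it adds "A transient, reversible sensation of altered or unusual taste, lasted 30 minutes in all cases at higher doses of Artesunate".

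**The concern.** One sentence of Section 3.1 names three effects, "mild gastrointestinal disturbances, dizziness, and tinnitus", and Table 5 solicits the second and third but not the first. No reason is given. The infusion row, by contrast, corresponds to nothing reported in Section 3.1, and its grades 1 to 3 are worded around interrupting an infusion, so they cannot be applied to a suppository.

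Mild symptoms that are asked about tend to be reported more completely than those left to the participant to raise. At stake is how complete and even the low-grade tolerability record is in a first study of this route, for which Section 3.1 says no published pharmacologic data exist. Evenness matters because Section 10.3 gives cohorts III and IV more early visits than cohorts I and II, and so more chances to mention an unprompted complaint.

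**Working it through.** The plan states no figure that rests on the symptom list, so there is none to reproduce. The main check sets the passages side by side.

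| Effect | Where Section 3.1 reports it | Row in Table 5 | Other named prompt (Section 7.1 or visit checklist) |
|---|---|---|---|
| Dizziness | Text | Yes | Section 7.1 |
| Tinnitus | Text | Yes | None by name |
| Headache | Table 2, oral | Yes | None by name |
| Hypersensitivity | Text | Yes | None by name |
| Gastrointestinal disturbance | Text; Table 2, rectal | No | Tenesmus only |
| Abdominal pain | Table 2, oral | No | Pain, site not stated |
| Flu-like syndrome | Table 2, oral | Partly (fever, headache) | None |
| Altered taste | Table 2, higher intravenous doses only | No | None |
| Infusion reaction | Not reported | Yes | None |

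**Does Section 7.1 close the gap?** Its list is the named symptoms plus unexpected events. The AE Reporting part of Section 11.7 defines an unexpected event as one not listed in available sources, and counts the protocol as a source. Gastrointestinal and taste effects are listed in Section 3.1. Read with that definition, they are neither named in 7.1 nor unexpected. The definition was written for reporting to oversight bodies, so applying it to 7.1 is an inference, but no other definition is given.

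**Are the events lost?** No. Section 11.7 requires all adverse events to be recorded through 30 days after the final treatment and graded by CTCAE v4.0. Section 12.4 tabulates all toxicities. Section 11.8 makes a grade 3 toxicity in any organ system dose-limiting. What these sections do not supply is a prompt for a mild or brief symptom.

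**Scale, as illustration only.** Inputs: Table 2 gives possibly drug-related events in about 2.7% to 9.0% of rectally treated patients; the synopsis plans 30 women; the captured fraction *s* is my assumption, tried from 1 down to 0.25. Expected count = 30 × *r* × *s*; P(at least one) = 1 − (1 − *rs*)^30.

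| *s* | *r* = 2.7%: expected, P(≥1) | *r* = 9.0%: expected, P(≥1) |
|---|---|---|
| 1 | 0.81, 56.0% | 2.70, 94.1% |
| 0.5 | 0.40, 33.5% | 1.35, 74.9% |
| 0.25 | 0.20, 18.4% | 0.67, 49.5% |

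In the three-woman run-in with full capture, P(at least one) is 1 − 0.973³ = 7.9% to 1 − 0.91³ = 24.6%.

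These figures do not measure the defect. The rate covers all possibly drug-related events and several artemisinin drugs, with no gastrointestinal share, and the table applies *s* even to symptoms that Table 5 does solicit. If the rectal trials relied on spontaneous reports, the rate already reflects unprompted capture and *s* discounts it twice.

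**The case against.** The strongest reply is that Table 5 is not the primary outcome. Adverse events of every kind count, prompted or not. Section 11.4 has patients document any adverse event, Section 11.5 tells them to contact staff between visits, and Table 3 checks adverse events at every visit from week 0. The diary card itself is not in the documents; it may carry more items than Table 5, or free text. Unlocated pain is already monitored, and fever and headache cover part of a flu-like illness. The infusion row is a leftover that suppresses no data.

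Most of this stands, and it rules out several stronger readings that a reader might infer:

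- *The primary outcome under-counts.* Not shown, for the reasons above.
- *The omitted symptoms are the likeliest systemic effects.* Section 3.1 calls the association weak, pools rectal gastrointestinal events with non-specific ones, reports taste change only at higher intravenous doses, and expects little systemic absorption by the vaginal route.
- *Solicited symptoms are the only direct check on absorption, or can serve as an index of uptake.* Symptoms do not measure exposure. Table 5 already asks about other systemic symptoms, and the synopsis promises weekly blood-cell monitoring (Table 3 shows no row for it, which is a separate matter).
- *The infusion row describes something impossible here.* That holds only for the infusion wording. Nothing in the documents excludes a cytokine-type reaction.

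The reply does not explain why the list takes some effects from the review and leaves out others, and a duty to record known events does not prompt a participant to mention them.

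**Conclusion.** The mismatch between Table 5 and Section 3.1 is established from the text. Its consequence is limited: low-grade gastrointestinal, flu-like and taste events may be captured less completely, and less evenly across cohorts, than the symptoms that are solicited. Grade 3 events remain dose-limiting, and no bias in the primary conclusion is demonstrated. The size cannot be computed from the documents.

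The conclusion rests on two assumptions: that the diary card, which I have not seen, follows Table 5 rather than going beyond it, and that prompting improves reporting of mild symptoms. If the card already lists these symptoms, what remains is to align Table 5 and Section 7.1 with it. This is a cheap improvement, not a design failure.

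A related inconsistency affects how much mild events matter. Section 3.2 makes escalation after cohort I depend on there being no reported mucosal or systemic adverse event, with no grade threshold, whereas Section 12.1 makes it depend on there being no dose-limiting toxicity. Under Section 3.2 one mild systemic complaint could bear on the decision; under Section 12.1 it could not. The two passages must be reconciled.

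**What to change.** In Table 5, the diary card and the Section 7.1 list, add solicited items for nausea/vomiting, diarrhoea, abdominal pain, flu-like symptoms and altered taste, graded by CTCAE v4.0, which Section 11.7 already uses. Remove the infusion wording from the cytokine-release row, or state why it is kept. In Section 12.4, say that solicited symptoms will be summarised by cohort and grade, separately from unsolicited events. Separately, reconcile Sections 3.2 and 12.1 on the cohort I decision.

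The cost is wording on the protocol, diary and case report form, with no extra visit, test or sample. The downside is that a longer prompt list will bring in more mild background complaints, so the reported rates will look slightly less favourable. With no control arm, the report should say so.
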